4.7.1 Adverse Events

Adverse events data will be coded using the Medical Dictionary for Regulatory Activities (MedDRA 19.1). Adverse events will be graded using the NCI CTCAE, Version 4.03.

A treatment-emergent adverse event (TEAE) is defined as any AE that starts on or after the first dose of study drug or occurs prior to the first dose and worsens in severity on or after the first dose of study drug, during the treatment period and follow-up period.

For AEs with partial start dates, non-missing date parts will be used to determine if the AE is treatment-emergent or not. If a determination cannot be made using the non-missing date parts as to when the AE occurred relative to study drug administration, e.g. AE start year and month are the same as the year and month of the first dose of investigational product, then the AE will be classified as treatment-emergent. See [Appendix B](#) for details on imputation rules.

An overview of TEAEs will be provided. The overview will summarize the subject incidence of the following information:

- Any TEAEs
- Worst NCI CTCAE grade of TEAEs
- Drug-related TEAEs
- Worst NCI CTCAE grade of drug-related TEAEs
- Any study drug-related Grade 3 or greater TEAEs
- TE-SAEs
- Drug-related TE-SAEs
- TEAEs leading to discontinuation of study drug
- Drug-related TEAEs leading to discontinuation of study drug
- TEAEs leading to study drug interruption
- Drug-related TEAEs leading to study drug interruption
- TEAEs leading to study drug dose reduction
- Drug-related TEAEs leading to study drug reduction
- Death

TEAEs will also be summarized using SOC, preferred term and SOC, preferred term and severity grade based on NCI CTCAE (Version 4.03). Drug-related TEAEs will be summarized in the same manner. IRR related AEs will be summarized separately.

The incidence and percentage of subjects with at least 1 occurrence of a preferred term will be included, using the most severe grade. The number of events per preferred term will also be summarized. Causality (relationship to study drug) will be summarized separately.

TEAEs, SAEs, deaths and AEs leading to withdrawal, dose reduction, dose interruption, or treatment discontinuation will be listed. Duration of AEs will be determined and included in listings, along with action taken and outcome.

4.7.2 Clinical Laboratory Tests

Laboratory results, percentage change and absolute change from baseline will be summarized by cohort, visit and time point using descriptive statistics. Incidence of laboratory abnormalities and laboratory NCI CTCAE (Version 4.03) will be summarized. Shift tables of CTCAE Grade for chemistry parameters (Normal, Grade 1, Grade 2, Grade 3, Grade 4, Grade 3/4, Total, Missing) from baseline to each post-baseline time point showing number and percentage of subjects with movement between categories will be presented. The worst on-study grade after the first study drug administration will also be summarized.

Baseline is defined as the Day 0 (pre-dose) measurement. If the baseline measurement is missing, the last measurement prior to the first study drug administration will be used.

Results, normal limits of the local laboratory, and abnormality flags will be listed.

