### 5.2 Inclusion Criteria

A subject must meet the following criteria to be eligible for the study:

1. Willing and able to read, understand and sign an informed consent form.
2. Male or female  $\geq 18$  years of age at the time of screening.
3. Confirmed diagnosis by enrolling physician of WAIHA, including positive direct Coombs test.
4. Hemoglobin  $< 11$  g/dL.
5. Evidence of active hemolysis including any one of the below:
  - a. LDH  $>$  upper limit of normal (ULN) or
  - b. Haptoglobin  $<$  lower limit of normal (LLN) or
  - c. Indirect bilirubin  $>$  ULN.
6. Other treatments for WAIHA:
  - a. If treated with rituximab or other anti-CD20 mAb, last dose  $> 3$  months prior to screening (a dose is defined as  $\geq 10\%$  of the intended dose).
  - b. If being treated with other immunosuppressants (ie, azathioprine, mycophenolate mofetil, methotrexate, cyclosporine, tacrolimus, sirolimus, or low-dose oral cyclophosphamide [ $\leq 100$  mg/day]), dose must be stable ( $< 25\%$  change in dose) for the 4 weeks prior to screening.
  - c. If being treated with corticosteroids, dose must be  $\leq 1$  mg/kg/day of prednisone or equivalent, and the dose may not be increased by more than 50% in the 2 weeks prior to screening.
  - d. No pulse corticosteroids are allowed in the 2 weeks prior to screening.
7. Treatment of chronic lymphocyte leukemia (CLL) or non-Hodgkin lymphoma (NHL) must be:
  - a. FDA-approved for oral treatment, and
  - b. Stable ( $< 10\%$  change in dose) for 6 weeks prior to screening; Bruton's tyrosine kinase inhibitor dose must be stable ( $< 10\%$  change in dose) for 8 weeks prior to screening.
8. Body mass index (BMI)  $> 18.5$  kg/m^2.
9. Has a negative pregnancy test (for women of childbearing potential) documented prior to the first dose of study drug.
10. Females of childbearing potential must agree to be abstinent or else use any two of the following medically acceptable forms of contraception ( $< 1\%$  per year failure rate) from the screening period through the final study visit: oral contraceptive, condom with or without spermicidal jelly, diaphragm or cervical cap with spermicidal jelly, or intra-uterine device (IUD). A female whose male partner has had a vasectomy must agree to use one additional form of medically acceptable contraception.

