## **11.5 Safety Analysis**

The evaluation of SYNT001 based on vital signs, physical examination, ECGs, clinical safety laboratory tests, the incidence of AEs, TEAEs, and SAEs will be summarized by dose and dose regimen, severity, and relationship to study drug.

Treatment-emergent AEs will be summarized using the Medical Dictionary for Regulatory Activities (MedDRA®; Version 19 or higher) System Organ Class (SOC) and preferred term, classified from verbatim terms. The incidence and percentage of subjects with at least 1 occurrence of a preferred term will be included, using the most severe grade. The number of events per preferred term will also be summarized. Causality (relationship to study drug [related/not related]) will be summarized separately.

TEAEs, SAEs, and AEs leading to withdrawal, dose modification, or treatment discontinuation will be listed by subject per SOC and preferred terms. Duration of AEs will be determined and included in listings, along with action taken and outcome.

Laboratory results will be summarized by time point, dose, and dose regimen. Incidence of laboratory abnormalities will be summarized. The worst on-study grade after the first dose of study drug will be summarized. Results for variables that are not coded will be presented in the listings as below, within, and above the normal limits of the central laboratory.

Vital sign measurements and change from baseline will be summarized at each scheduled time point by cohort using descriptive statistics.

Arithmetic mean of parameters from triplicate ECG will be calculated first for each participant at each planned time point. Then summary statistics of ECG test parameters (mean of triplicate) and change from baseline to each post-dose time point will be calculated. Shift tables for ECG test result category change (normal, abnormal, clinically abnormal) from pre-dose to each post-dose time point showing number and percentage of subjects with movement between categories will be presented by treatment group. Frequency and percentage of subjects experiencing potential QTc prolongation (QTcF >450) will be summarized at each time point by cohort.

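### SAP 4.7.2 gives hematology no graded comparison with baseline, although every subject enters anemic; separately, its listing names local rather than central laboratory limits

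*SAP*

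**What the plan says.** SAP 4.7.2 describes the following laboratory outputs.

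- Continuous summaries: "Laboratory results, percentage change and absolute change from baseline will be summarized by cohort, visit and time point using descriptive statistics". These cover hematology.
- Incidence: "Incidence of laboratory abnormalities and laboratory NCI CTCAE (Version 4.03) will be summarized". No condition of being new or worse than baseline is attached.
- Worst grade: "The worst on-study grade after the first study drug administration will also be summarized". Baseline grade is not mentioned.
- Shift from baseline to each post-baseline time point: "Shift tables of CTCAE Grade for chemistry parameters". Hematology is not named.
- Listing: "Results, normal limits of the local laboratory, and abnormality flags will be listed".

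The SAP treats adverse events differently. Under SAP 4.7.1, an event counts as treatment-emergent if it starts on or after the first dose, or if it "occurs prior to the first dose and worsens in severity on or after the first dose of study drug".

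On the population, protocol 5.2 requires hemoglobin below 11 g/dL of every subject (criterion 4). Criterion 5 adds "Evidence of active hemolysis including any one of the below": raised LDH, low haptoglobin or raised indirect bilirubin. Protocol 5.3 excludes platelet counts only below 30 x 10^9/L.

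On the laboratory, SAP 3.2.7 and protocol 6.7 assign testing to a central laboratory. Protocol 6.7 allows a local laboratory only for retests at screening. Protocol 11.5 lists results for variables that are not coded as "below, within, and above the normal limits of the central laboratory".

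**The concern.** Clinical safety laboratory tests are part of the primary safety endpoint. The trial has no control arm, so each subject's own baseline is the only comparator for a laboratory change. Where baseline values are mostly normal, a count of post-dose abnormalities approximates a count of new ones. That is not so here: anemia is an entry condition, and low platelets are permitted.

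A hematology incidence or worst-grade table that ignores baseline grade cannot tell a subject who entered at a given grade and stayed there from one who reached it after dosing. A shift table makes that distinction, and the SAP provides one for chemistry and for ECG categories (SAP 4.7.3) but not for hematology. It gives no reason for the difference.

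The local-laboratory wording is a separate and smaller matter. If central results were paired with local ranges across about 15 sites (protocol 4.1), the same value could be flagged at one site and not at another.

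**Working it through.** The documents give no power, error-rate or event figure on this point (SAP 5 states that no formal sample size calculation was made), so there is no figure to reproduce. The check is a reading of the text, with an illustration of size.

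**1. Which outputs compare hematology with baseline?**

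| Output in SAP 4.7.2 | Covers hematology | Refers to baseline |
|---|---|---|
| Absolute and percent change | yes | yes, continuous only |
| Abnormality and grade incidence | yes | no |
| Worst grade after first dose | yes | no |
| CTCAE grade shift | no, chemistry only | yes |

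No row is at once graded, referenced to baseline and applied to hematology. SAP 4.8.2 adds change summaries and plots for hemoglobin, hematocrit, platelets and reticulocytes, which are again continuous.

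**2. Which entry abnormalities are involved?** Only low hemoglobin is required of everyone. Low platelets are allowed but not required. The hemolysis markers are alternatives, so no single one is common to all subjects. LDH and bilirubin are in the chemistry panel (protocol Table 6), where the shift tables apply. Haptoglobin is outside the safety panel.

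**3. Size if nothing changes.** Inputs: up to 8 + 12 = 20 subjects (protocol 6.8). Assumption: every Day 0 hemoglobin is below the lower limit of normal. The documents give neither that limit nor the CTCAE cut-offs.

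- No subject changes grade: incidence as planned 20/20 (8/8 and 12/12); count of grades worse than baseline 0/20.
- 25% of subjects are normal at every post-dose draw and none worsens: 20 x (1 - 0.25) = 15/20 against 0/20.
- 50% are normal at every post-dose draw and none worsens: 20 x (1 - 0.50) = 10/20 against 0/20.

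**4. How easily is a subject counted?** A subject anemic at entry stays out of the incidence count only if every post-dose hemoglobin is normal. The schedules give 9 post-dose safety draws in Cohort 1 (Days 7, 14, 21, 28, 33, 42, 56, 84, 112) and 9 in Cohort 2 (Days 7, 14, 28, 42, 56, 70, 84, 91, 140). The alternative weekly schedule gives 14 (weekly from Day 7 to Day 84, which is 12, plus Days 91 and 140). Let q be an assumed chance of a normal value at each draw, with draws assumed independent. The chance of being counted is 1 - q^n.

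| q | n = 9 | n = 14 |
|---|---|---|
| 0.5 | 99.8% | 99.99% |
| 0.8 | 86.6% | 95.6% |
| 0.9 | 61.3% | 77.1% |

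These values of q are assumptions. They show direction and range and are not forecasts.

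**5. Granularity.** One subject who enters with low platelets and does not change adds 1/8 = 12.5 percentage points to a Cohort 1 row, or 1/12 = 8.3 to a Cohort 2 row. Any single subject carries that weight in any table of this trial, so this describes the scale of the tables and does not measure the defect.

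**6. Which laboratory?** Testing is central (SAP 3.2.7, protocol 6.7), and protocol 11.5 uses central limits. The SAP 4.7.2 listing uses local limits. SAP 1 says that substantial departures from the protocol will be identified, and this one is not. The listing sentence is the only place in SAP 4.7.2 that names the source of the limits.

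**The case against.** The strongest defense is that baseline is not ignored. Absolute and percent change cover hematology by cohort, visit and time point, and all data are listed. With at most 20 subjects, a reader can trace each one by hand. This is true, but means in cohorts of 8 or 12 can hide one subject's move from a low to a high grade, and tracing listings by hand is not a planned summary.

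A second defense also stands in part. Clinically significant laboratory abnormalities are recorded as adverse events (protocol 6.7, SAP 3.2.7), values consistent with those before entry are exempted (protocol 10.4.1), and the treatment-emergent definition requires onset or worsening after dosing. The adverse event tables are therefore sound. That route depends on a judgment of clinical significance, however, and the laboratory tables are meant to show graded values without it.

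Third, mock tables and derived-data specifications are in separate documents (SAP 6), which might supply an emergence rule. They may, but the SAP itself states that the shift tables are for chemistry, and that is a stated choice rather than a missing detail.

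A reader might go further and infer that the hemoglobin abnormality rate will be close to 100% whatever the drug does. The documents do not support this. Eligibility is judged at screening, up to 14 days (Cohort 1) or 28 days (Cohort 2) before Day 0, sustained normalization would lower the rate, and the illustration itself runs from 61.3% to 99.99%. Nor is the worst-grade table saturated: a move to a higher grade still changes it. What the table lacks is the baseline grade needed to interpret the move.

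**Conclusion.** The point holds within limits. In SAP 4.7.2 hematology has no graded comparison with baseline, in a population where anemia is an entry condition and low platelets are permitted. The hematology incidence and worst-grade tables would mix pre-existing with new or worsened abnormalities. In the no-change case the gap is 20/20 against 0/20. That rests on the assumption that Day 0 hemoglobin is still below a lower limit of normal that the documents do not give. Continuous hematology summaries and the treatment-emergent adverse event tables are unaffected.

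Two wider readings should be resisted. A reader might infer that the hematology tables as a whole merely restate the entry criteria. Only hemoglobin is required to be low, and no neutrophil or lymphocyte entry limit is set. A reader might also infer that abnormality rates are calculated from the wrong laboratory's limits. The local wording is confined to the listing sentence, and SAP 4.7.2 does not say which limits lie behind the incidence table. What is established is a conflict in wording with the protocol and with central testing.

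The change should be made, because it concerns a stated analysis of a primary safety component and costs almost nothing.

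**What to change.** In SAP 4.7.2:

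1. Extend the CTCAE shift tables to hematology parameters, and add a shift from baseline grade to worst post-baseline grade.
2. Beside the count of all abnormalities, present a treatment-emergent count, defined as a post-baseline grade higher than the baseline grade. Keep both, since the full count remains a fair description in a single-arm study.
3. In the listing sentence, change *local* to *central* laboratory, and use local limits only for values actually tested locally (screening retests).

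The cost is revised SAP wording and a few extra tables from data already collected, with no new visits, samples or subjects.

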4.7.3 Physical Examination, Vital Signs, and Electrocardiogram Findings

The number and percentage of subjects with normal, abnormal and clinically significant, abnormal but not clinically significant physical exam findings will be summarized by visit and dose.

Vital sign measurements and change from baseline will be summarized at each scheduled time point by cohort using descriptive statistics. Baseline is defined as the Day 0 (pre-dose) measurement. If the baseline measurement is missing, the last measurement prior to the first study drug administration will be used.

The arithmetic mean of parameters from triplicate ECGs will be calculated first for each participant at each planned time point. Then summary statistics for ECG test parameters (mean of triplicate) and change from baseline to each post-dose time point will be calculated. Shift tables for ECG test result category changes (normal, abnormal not clinically significant, abnormal clinically significant) from pre-dose to each post-dose time point showing number and percentage of subjects with changes between categories will be presented by cohort.

The number and percentage of subjects experiencing potential QTcF prolongation (QTcF > 450, >480 and >500 msec, and change from baseline in QTcF >30 and >60 msec) will be summarized at each time point by cohort.

Actual sampling times that are outside the scheduled sampling times window described in [Table 5](#) will be excluded from summary statistics.

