- b. **Vital sign** measurements (sitting blood pressure, heart rate, respiratory rate, and oral temperature) to be obtained after 5 minutes of seated rest. Any abnormal measurements are to be repeated after 5 minutes of rest. Vital sign measurements will be taken on all study visits. On dosing days, vital sign measurements will be collected immediately prior to the infusion; 15, 30, and 45 minutes after the start of the infusion; at completion of the infusion; and 30 minutes, 1 hour and 2 hours following completion of the infusion.
- c. **Pulse oximetry**: On dosing day, pulse oximetry to be measured immediately prior to the infusion; 15, 30, and 45 minutes after the start of the infusion; at completion of the infusion; and 30 minutes, 1 hour, and 2 hours following completion of the infusion.
- d. **Clinical safety labs**: hematology, clinical chemistry, and urinalysis. See Section 6.7 for a complete list. Full clinical safety lab draws will be collected at screening and at all study visits prior to infusion if applicable. PD markers (albumin levels, hematocrit, hemoglobin, platelet count, reticulocyte count, lactate dehydrogenase, and total and indirect bilirubin) will be derived from the clinical safety laboratory results.
- e. **Pregnancy test (women of childbearing potential only)**: To be performed at time of screening and prior to dose on dosing days if applicable. Urine or serum test is acceptable; however, positive urine tests must be confirmed with serum testing.
- f. Digital 12-lead **ECG** to be obtained after 5 minutes of rest in the supine position and in triplicate approximately 1 minute apart. See Section 6.6 for additional information. On days of treatment, to be obtained 5 minutes after the completion of infusion.
- g. **Serology**: Any subject whose baseline value for tetanus or VZV was above the protective level at baseline and is not within 30% of the baseline value or is below the protective level by End of Follow-up, will be referred to their primary care physician for further management. See Section 6.7.3 for additional information.
- h. **PK**: Starting on dosing days, serum samples will be collected just prior to the start of study drug infusion (pre-dose) and at 5 minutes, 1 and 2 hours after the end of study drug infusion. See Section 6.7.4 for additional information.
- i. **Immunogenicity**: Samples will be collected pre-dose when collected on dosing days. See Section 6.7.6 for additional information.

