4.7 Safety Analyses

All statistical analysis of safety outcomes will be descriptive. Safety observations and measurements include AEs, treatment-emergent AEs (TEAEs), SAEs, safety laboratory tests, vital sign measurements, PEs, and ECGs. The incidence of AEs, TEAEs and SAEs will be summarized by cohort, severity and relationship to study product. Baseline for safety parameters is defined as Day 0 (pre-dose) measurement. If missing, the last measurement prior to the first study drug administration will be used as the baseline value.

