- c. Vital sign measurements (sitting blood pressure, heart rate, respiratory rate, and oral temperature) to be obtained after 5 minutes of seated rest. Any abnormal measurements are to be repeated after 5 minutes of rest. On Days 0, 7, 14, 21, and 28, vital sign measurements will be collected immediately prior to the infusion; 15, 30, and 45 minutes after the start of the infusion; at completion of the infusion; and 30 minutes, 1 hour, and 2 hours following completion of the infusion.
- d. Pulse oximetry: On Days 0, 7, 14, 21, and 28, pulse oximetry to be measured immediately prior to the infusion; 15, 30, and 45 minutes after the start of the infusion; at completion of the infusion; and 30 minutes, 1 hour and 2 hours following completion of the infusion.
- e. Clinical safety labs: hematology, clinical chemistry, and urinalysis. See Protocol Section 6.7 for a complete list. Full clinical safety laboratory draws will be collected at screening and on Days 0, 7, 14, 21, 28, 33, 42, 56, 84, and 112. PD markers (albumin levels, hematocrit, hemoglobin, platelet count, reticulocyte count, lactate dehydrogenase, and total and indirect bilirubin) will be derived from the clinical safety laboratory results.
- f. Pregnancy test (women of childbearing potential only): To be performed at time of screening, prior to first dose of SYNT001 on Day 0, and on Days 56 and 112. Urine or serum test is acceptable; however, positive urine tests must be confirmed with serum testing.
- g. Digital 12-lead ECG to be obtained in triplicate at least 1 to 2 minutes apart and after 5 minutes of rest in a supine position. See Protocol Section 6.6 for additional information. On Days 0 and 28 to be obtained 5 minutes after the completion of infusion. Day 12 ECG will be collected only if the visit is conducted at the study site.

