- b. Vital sign measurements (sitting blood pressure, heart rate, respiratory rate, and oral temperature) to be obtained after 5 minutes of seated rest. Any abnormal measurements are to be repeated after 5 minutes of rest. Vital sign measurements will be taken on all study visits. On dosing days, vital sign measurements will be collected immediately prior to the infusion; 15, 30, and 45 minutes after the start of the infusion; at completion of the infusion; and 30 minutes, 1 hour and 2 hours following completion of the infusion.
- c. Pulse oximetry: On dosing day, pulse oximetry to be measured immediately prior to the infusion; 15, 30, and 45 minutes after the start of the infusion; at completion of the infusion; and 30 minutes, 1 hour, and 2 hours following completion of the infusion.
- d. Clinical safety labs: hematology, clinical chemistry, and urinalysis. See Protocol Section 6.7 for a complete list. Full clinical safety lab draws will be collected at screening and at all study visits prior to infusion if applicable. PD markers (albumin levels, hematocrit, hemoglobin, platelet count, reticulocyte count, lactate dehydrogenase, and total and indirect bilirubin) will be derived from the clinical safety laboratory results.
- e. Pregnancy test (women of childbearing potential only): To be performed at time of screening and prior to dose on dosing days if applicable. Urine or serum test is acceptable; however, positive urine tests must be confirmed with serum testing.
- f. Digital 12-lead ECG to be obtained after 5 minutes of rest in the supine position and in triplicate approximately 1 minute apart. See Protocol Section 6.6 for additional information. On days of treatment, to be obtained 5 minutes after the completion of infusion.
- g. Serology: Any subject whose baseline value for tetanus or VZV was above the protective level at baseline and is not within 30% of the baseline value or is below the protective level by End of Follow-up, will be referred to their primary care physician for further management. See Protocol Section 6.7.3 for additional information.
- h. PK: Starting on dosing days, serum samples will be collected just prior to the start of study drug infusion (pre-dose) and at 5 minutes, 1 and 2 hours after the end of study drug infusion. See Protocol Section 6.7.4 for additional information.
- i. Immunogenicity: Samples will be collected pre-dose when collected on dosing days. See Protocol Section 6.7.6 for additional information.

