- o. Immunophenotyping by flow cytometry for measurement of CD3⁺CD4⁺ T, CD3⁺CD8⁺ T, monocytes, natural killer (NK) cells, and B cells. Collect samples pre-dose on dosing days

Table 5. Timing window allowances for PK/PD sampling, ECG, and vital sign measurements at dosing visits

Time Point	Tolerance Window	
	Cohort 1	Cohort 2
Pharmacokinetic Sampling		
0 hour	-240 minutes to 0 hour	-240 minutes to 0 hour
5 minutes post end-of-infusion	±5 minutes	±5 minutes
1 hour post end-of-infusion	N/A	±15 minutes
2 hours post end-of-infusion	±15 minutes	±15 minutes
4 and 6 hours post end-of-infusion	±15 minutes	N/A
24 hours post end-of-infusion	±60 minutes	N/A
48 hours post end-of-infusion	±120 minutes	N/A
Pharmacodynamic (Immunoglobulins) Sampling		
0 hour	-240 minutes to 0 hour	-240 minutes to 0 hour
24 hours post end-of-infusion	±60 minutes	N/A
48 hours post end-of-infusion	±120 minutes	N/A
ECG		
5 minutes post end-of-infusion	±10 minutes	±10 minutes
Vital Signs^a		
0 hour	-240 minutes to 0 hour	-240 minutes to 0 hour
15, 30, and 45 minutes after start of infusion	±5 minutes	±5 minutes
At completion of the infusion	±10 minutes	±10 minutes
30, 60, and 120 minutes post end-of-infusion	±10 minutes	±10 minutes

Abbreviations: ECG = electrocardiogram; PD = pharmacodynamic; PK = pharmacokinetic.

^aVital signs to include blood pressure, pulse rate, respiratory rate, oral temperature, and pulse oximetry (Cohort 1 only).

Table 6. Pharmacodynamic Assessments

Parameter	Collection Time Points	
	Cohort 1	Cohort 2 ^a
Immunoglobulins: IgG IgG subtypes (IgG1-4) IgA IgM	Screening and Days 0, 1, 2, 5, 7, 12, 14, 19, 21, 28, 29, 30, 33, 42, 56, 84, and 112	Screening and Days 0, 7, 14, 28, 42, 56, 70, 84, 91, 112, 140
Circulating immune complexes (CIC)	Days 0, 5, 7, 12, 14, 19, 21, 28, 33, 42, 56, 84, and 112	Days 0, 7, 14, 28, 42, 56, 70, 84, 91, 112, 140
Albumin Hematocrit Hemoglobin Haptoglobin Platelet count Reticulocyte count Lactate dehydrogenase (LDH) Total and indirect bilirubin	Screening and Days 0, 7, 14, 21, 28, 33, 42, 56, 84, and 112	Screening and Days 0, 7, 14, 28, 42, 56, 70, 84, 91, 140
Direct Coombs test (also known as direct antiglobulin test [DAT])	Screening and Days 0, 14, 33, 56, 84, and 112	Screening and Days 0, 14, 28, 91, 140

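### From the second infusion on, vital-sign change during and after an infusion is measured from Day 0, so the planned change summary mixes between-visit drift with the infusion effect.

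*SAP*

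**What the plan says.** SAP 4.7.3 gives the whole vital-sign analysis: "Vital sign measurements and change from baseline will be summarized at each scheduled time point by cohort using descriptive statistics". The reference value follows: "Baseline is defined as the Day 0 (pre-dose) measurement". The fallback is also a pre-treatment value: "If the baseline measurement is missing, the last measurement prior to the first study drug administration will be used". SAP 4.7 sets the same rule more generally: "Baseline for safety parameters is defined as Day 0 (pre-dose) measurement". Protocol 11.5 plans the same change-from-baseline summary and names no reference for individual infusions.

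The readings around each infusion are scheduled time points. SAP Table 5 lists them with tolerance windows, for example "15, 30, and 45 minutes after start of infusion". The schedule notes in SAP Appendix A continue with readings "at completion of the infusion; and 30 minutes, 1 hour and 2 hours following completion of the infusion".

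A fresh pre-infusion reading is taken at every dosing visit. For Cohort 1, SAP Table 2 says: "On Days 0, 7, 14, 21, and 28, vital sign measurements will be collected immediately prior to the infusion". For Cohort 2, Protocol Table 3 says: "On dosing days, vital sign measurements will be collected immediately prior to the infusion". Neither document uses that reading as the reference for the same day's later readings.

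**The concern.** Eight readings per infusion, seven of them after the start, are suited to showing what the infusion does to heart rate, blood pressure, temperature, respiration and oxygen saturation. Protocol 9.6.2 lists changes in heart rate and blood pressure among the symptoms of infusion reactions. The natural question is how far a reading moved from its level just before that infusion. From the second infusion on, the planned change score answers a different question: how far it moved from its level before the first dose.

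Drift between visits is plausible here. Subjects enter with hemoglobin below 11 g/dL and active hemolysis, the drug is meant to reduce hemolysis, and transfusions occur and are counted. There is no control arm to separate drift from drug effect. Vital signs are a named component of the primary safety endpoint, and with up to 8 and up to 12 subjects the spread and the extremes matter as much as the mean.

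**Working it through.** The plan states no figure to reproduce; no sample size, SD or effect size is given. The check is a count, an identity and a variance formula.

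**1. Infusions affected.** Dosing days come from SAP Tables 2 to 4. With n infusions, Day 0 is the same-day reference only for the first, so n − 1 are affected. Each infusion has 7 in- and post-infusion readings (15, 30 and 45 minutes; completion; 30 minutes, 1 hour and 2 hours after).

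| Schedule | Infusions affected | Readings affected | Longest nominal lag |
|---|---|---|---|
| Cohort 1 | 4 of 5 (80%) | 28 of 35 | Day 28 = 4 weeks |
| Cohort 2, every other week | 7 of 8 (87.5%) | 49 of 56 | Day 84 = 12 weeks |
| Cohort 2, weekly | 12 of 13 (92.3%) | 84 of 91 | Day 84 = 12 weeks |

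With the +3-day window the Cohort 2 lag is 87/7 = 12.4 weeks. If Day 0 is missing and a Day −28 screening reading is substituted, it is (84 + 28)/7 = 16 weeks.

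**2. What the change score contains.** For a reading at time t on dosing day d:

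reading(d, t) − Day 0 = [pre-infusion(d) − Day 0] + [reading(d, t) − pre-infusion(d)] = drift + infusion effect.

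This needs no assumption. Illustration: with a drift of −10 bpm and a rise of +15 bpm during the infusion, the score at that time point is −10 + 15 = +5.

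**3. What the tables still show.** The pre-infusion reading is itself a scheduled time point, so its row shows the mean drift (−10 in the illustration). Subtracting rows gives the mean infusion effect: +5 − (−10) = +15. This is exact only if the same subjects contribute to both rows. They may not, because SAP 4.7.3 drops readings outside the Table 5 windows from summary statistics.

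Subtraction does not give the distribution. Take two subjects with the same Day 0 value and pre-infusion changes of −10 and 0. If their 15-minute changes are also −10 and 0, the within-infusion changes are 0 and 0. If the 15-minute changes are instead 0 and −10, the within-infusion changes are +10 and −10. Both cases give identical summaries in both rows, yet the largest within-infusion rise is 0 in one and +10 in the other.

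**4. Precision.** If readings have equal SD σ, the SD of a difference is σ√(2(1 − r)). The variance ratio, Day 0 reference to same-day reference, is (1 − r_between)/(1 − r_within). The documents give neither correlation, so both are assumptions:

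| r_between | r_within | Variance ratio |
|---|---|---|
| 0.5 | 0.5 | 0.5/0.5 = 1.0 |
| 0.5 | 0.6 | 0.5/0.4 = 1.25 |
| 0.5 | 0.8 | 0.5/0.2 = 2.5 |
| 0.7 | 0.8 | 0.3/0.2 = 1.5 |
| 0.3 | 0.8 | 0.7/0.2 = 3.5 |

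At 0.5 between and 0.8 within, the SDs are 1.00σ and 0.63σ.

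**The case against.** A single pre-treatment baseline is a conventional, explicit choice, and the SAP uses it consistently for vital signs, laboratory tests and safety parameters in general. Drift is displayed, since the pre-infusion row sits in the same summary. SAP 4 promises listings of all clinical data, and with at most 8 and 12 subjects anyone can work out each subject's within-infusion change. Infusion reactions have other outputs: adverse events related to them are summarised separately (SAP 4.7.1), medication for them is tabulated (SAP 4.5), and abnormal vital signs are CTCAE graded (SAP 3.2.5). Stopping rules rest on graded, drug-related events and clinical judgement, and no statistical analysis supports dose decisions. The same-day reading may be taken up to 240 minutes before the infusion (SAP Table 5), which could lower the within-visit correlation and with it any gain in precision.

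All of that stands. It rules out several stronger readings that a reader might infer: that every infusion is affected (the first is not, unless its Day 0 reading is missing), that 12 weeks applies to both cohorts, that infusion reactions would go undetected, or that individual changes are unrecoverable. It does not supply the missing summary. A listing lets a reader compute the SD and extremes of within-infusion change, but the planned tables do not report them. SAP 1 allows supplementary analyses without committing to this one.

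**Conclusion.** The point holds as a limitation of a planned descriptive summary. The mixing of drift and infusion effect in 80%, 87.5% or 92.3% of infusions, depending on schedule, follows from the SAP's definitions alone. The loss is the SD, median, minimum and maximum of within-infusion change for a component of the primary endpoint.

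Its practical size is unknown, because the documents contain no data on vital-sign drift or correlation. It would be tempting to say that the Day 0 reference inflates variance 2.5-fold. The documents do not support that as a finding: it is one cell of an assumed range that reaches 1.0 when the two correlations are equal, it presumes equal variance at rest and during infusion, and no planned test or interval depends on it. The change is worth making because it is nearly free, not because subject safety or a study decision is shown to depend on it.

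**What to change.** In SAP 4.7.3, keep the Day 0 baseline for change over the study. Add that, for time points from 15 minutes after the start to 2 hours after completion of each infusion, change from the same visit's pre-infusion value will also be summarised by cohort, visit and time point (n, mean, SD, median, minimum, maximum). Include pulse oximetry, which SAP 3.2.5 counts as a vital sign. The footnote to SAP Table 5 limits it to Cohort 1 while the schedules collect it in both cohorts, so those texts should be reconciled at the same time. State how a missing or out-of-window pre-infusion reading is handled, for example that no same-day change is then calculated.

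The cost is a sentence or two in the SAP and one more change column in the table shells, which SAP 6 finalises before database lock. No new data are needed and study conduct does not change.
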